**Table 11. Criteria for Treatment Emergent Potentially Clinically Significant Vital Signs**

Vital Sign Parameter	Flag	Criterion Value	Change from Baseline
Systolic Blood Pressure (mmHg)	High (CH)	≥ 180	Increase of ≥ 20 mmHg
	Low (CL)	<90	Decrease of ≥ 20 mmHg
Diastolic Blood Pressure (mmHg)	High (CH)	≥ 105	Increase of ≥ 15 mmHg
	Low (CL)	≤ 50	Decrease of ≥ 15 mmHg
Heart Rate (beats/min)	High (CH)	≥ 120	Increase of ≥ 15 beats/min
	Low (CL)	≤ 50	Decrease of ≥ 15 beats/min

## 9.0 CHANGES FROM THE PROTOCOL SPECIFIED ANALYSES

Two additional microbiologic Analysis Sets (microITT-2 and emicroITT) were included. The microITT-2 Analysis Set will consist of all subjects in the ITT Analysis Set who have at least 1 baseline bacterial pathogen known to cause CABP as defined in Sections 4.1 and 4.2 from a diagnostic method other than PCR. The emicroITT Analysis Set will consist of all subjects in the ITT Analysis Set who have at least 1 baseline bacterial pathogen known to cause CABP as defined in Sections 4.1 and 4.2, except a baseline pathogen from a sputum culture is defined using the presence of a Gram stain with ≥10 PMNs/LPF and <10 SECs/LPF rather than >25 PMNs/LPF and <10 SECs/LPF. Additional analyses performed in these Analysis Sets include summaries of the following: ECR (microITT-2 and emicroITT), ECR by baseline pathogen (microITT-2), IACR at TOC (microITT-2 and emicroITT), IACR at TOC by baseline pathogen (microITT-2), by-subject microbiologic response at TOC (microITT-2), and by-pathogen microbiologic response at TOC (microITT-2).

Other additional efficacy analyses specified in this SAP include summaries of the following: ECR by baseline pathogen and MIC or disk diffusion zone diameter to study drug received (microITT), ECR by baseline pathogen identified from blood (microITT), IACR at EOT and LFU (microITT and relevant ME Analysis Sets), IACR at EOT by baseline pathogen (microITT and ME-EOT), IACR at TOC by baseline pathogen and MIC or disk diffusion zone diameter to study drug received (microITT and ME-TOC), IACR at TOC by baseline pathogen identified from blood (microITT), by-subject and by-pathogen microbiologic response at EOT and LFU (microITT and relevant ME Analysis Sets), and by-pathogen microbiologic response at TOC by MIC or disk diffusion zone diameter to study drug received (microITT and ME-TOC).

**APPENDIX A: SCHEDULE OF ASSESSMENTS AND PROCEDURES**

Assessment or Procedure	Screening/	Study Drug Administration				EOT d	Follow-up Visits	
	Baseline a	Day 1 b	Day 2	Day 3	Days 4 to 7 c	Visit	TOC e	LFU f
Informed consent form completed g	X							
Verify inclusion/exclusion criteria	X							
Medical and surgical history	X							
Determine PORT Risk Class	X							
Height and weight	X							
Randomization	X							
Prior and concomitant medications	X	X	X	X	Daily	X	X	X
Vital signs including oxygen saturation and supplemental oxygen i	X	X	X	X	Daily	X	X	
CABP signs and symptoms j	X	X	X	X	Daily j	X	X	X
AEs and SAEs k	X	X	X	X	Daily	X	X	X
12-lead ECG l	X	X			Day 4 m			
Physical examination n	X				Day 4 o	X	X	
Hematology, clinical chemistry, urinalysis, procalcitonin (Central Lab) p	X h				Day 4 q	X	X	
Urine and serum pregnancy tests r	X	X						
CXR or CT scan	X							
Arterial blood gases (PaO 2 , PaCO 2 ) and pH [optional; record data if available]		if clinically indicated						
Calculate CrCl (Cockcroft-Gault formula)	X	if clinically indicated						
Urine sample for L. pneumophila and S. pneumoniae antigen tests	X h							
Blood sample for serologic tests for M. pneumoniae , C. pneumoniae , and L. pneumophila s	X h							X
Blood sample for culture t	X h	if clinically indicated						
Respiratory sample for Gram's stain and culture u	X h	if clinically indicated						
Pleural fluid and/or bronchoalveolar lavage (BAL) sample for Gram's stain and culture v		if clinically indicated						
Oropharyngeal and nasopharyngeal samples w	X h							
Administer SF-12 health status questionnaire	X h						X	
Study drug administration x		X	X	X	Daily			
Blood samples for PK analyses		Day 1 y			Day 4 y			

Assessment or Procedure	Screening/	Study Drug Administration				EOT d	Follow-up Visits	
	Baseline a	Day 1 b	Day 2	Day 3	Days 4 to 7 c	Visit	TOC e	LFU f
Investigator’s Assessment of Clinical Response (IACR) z						X	X	X

**NOTE:** Hospitalization is not a requirement for this study. However, all subjects, including Outpatients, must be evaluated at the investigational site by study personnel at the following time points/visits: Screening/Baseline; Day 1; Day 4 / 96 ± 24 hours after the first dose of study drug; EOT; TOC; and LFU.

- a: Perform Screening/Baseline assessments within 24 hours before the first dose of study drug. Administration of study drug should begin as soon as possible after the diagnosis of CABP. **See Footnote x.** Assessments performed as part of routine standard of care prior to consent (e.g., chest X-ray, blood culture) may be used to satisfy study screening requirements; however, no study specific procedures may be performed prior to informed consent.
- b: Day 1 is the first day of study drug administration; subsequent study days are consecutive calendar days. Assessments/ procedures on Day 1 should be performed prior to first dose.
- c: INPATIENTS will be assessed daily while hospitalized; thus, data required for ECR Assessment (96 ± 24 hours after the first dose of study drug) will be collected. **OUTPATIENTS must have a visit at the study site that is 96 ± 24 hours after the first dose of study drug to assess CABP signs and symptoms for calculation of ECR.** Study personnel will inform subjects as to the timing of this visit during the course of daily telephone contact. In addition to the assessment of CABP signs/symptoms, subjects will also have the following procedures/assessments performed at that study site visit: ECGs, physical examination, AE monitoring, review of concomitant medications, vital signs, oxygen saturation, and blood sampling for PK analysis and safety laboratory evaluations. Importantly, study personnel will advise OUTPATIENTS not to take their first dose of study drug at home that day, rather to bring their blister packs (used and unused) to the study site where they will take their dose while supervised; thus, specific assessments can be performed both prior to and after taking the dose (i.e., ECGs and PK). **See Footnotes i, k, l, m, o, p, and y below for details.**
- d: Perform End of Treatment (EOT) assessments at the study site within 1 day (up to 2 days permitted) after the last dose of study drug or at the time of premature discontinuation of study drug or early withdrawal from study. EOT assessments resulting from premature discontinuation of study drug should be done in place of the regular study visit on Days 1 to 7.
- e: Perform Test of Cure (TOC) assessments at the study site 5–10 days after the last dose of study drug. All subjects will have a TOC Visit irrespective of early clinical failure or receipt of an alternative antibiotic.
- f: Perform Late Follow Up (LFU) assessments at the study site on Day 30 ± 3 days. All subjects will have a LFU Visit irrespective of early clinical failure or receipt of an alternative antibiotic.
- g: Obtain informed consent before initiating any study-specific assessments or procedures.
- h: Assessment or procedure may occur at either Screening OR prior to the first dose of study drug on Day 1 once eligibility has been determined.
- i: All subjects will have vital signs and O2 saturation evaluated at Screening/Baseline and Day 1. If screening/baseline and Day 1 occur on the same calendar day, vital signs and O2 saturation do not need to be repeated. All subjects will also have assessments at EOT and TOC; at LFU, vital signs should be performed if medically indicated. If EOT and the last day of study drug are the same day, vital signs do not need to be repeated, they may be recorded once on that day (i.e., as part of the EOT assessment). Record the vital signs associated with the highest temperature after the first dose of study drug.  
**INPATIENTS:** Vital signs, O2 saturation, and supplemental O2 usage will be measured daily. If multiple vital signs are taken on a study day, the highest temperature and the vital signs associated with that high temperature will be recorded.  
**OUTPATIENTS:** In addition to the above time points, vital signs, O2 saturation and, if applicable, supplemental O2 usage will be measured at the study visit scheduled 96 ± 24 hours after the first dose of study drug.
- j: Study personnel will evaluate signs and symptoms of CABP at Baseline, daily while on study therapy, and at EOT, TOC, and LFU Visits. **NOTE:** If Screening and Day 1 are the same day, signs and symptoms of CABP do not need to be repeated on Day 1. If EOT and the last day of study drug are the same day, signs and symptoms of CABP should be done only once on that day (i.e., as part of the EOT assessment). Signs and symptoms are not obtained at TOC or LFU if the subject was previously deemed to have an IACR of Failure.  
**OUTPATIENTS:** Study personnel will contact subjects daily by telephone to track signs and symptoms of CABP; **however, subjects must report to the study site for the assessment of CABP signs/symptoms 96 ± 24 hours after the first dose of study drug.** *See Footnote c.*

- k: Record AEs from the signing of the ICF through TOC and SAEs from signing of the ICF through LFU. Study personnel will follow unresolved AEs and SAEs present at LFU until resolution or stabilization. In addition, study personnel will monitor AEs for OUTPATIENTS in conjunction with daily telephone contacts for CABP signs/symptoms and at the study site visit 96 ± 24 hours after the first dose of study drug. *See Footnote c.*
- l: **At each required time point, ECGs should be recorded in triplicate within a 5-minute interval.** The subject should be stabilized in a supine position for 5 min before recording the ECG. If Screening and Day 1 are on the same day, the Screening ECG can serve as the Day 1 ECG prior to the first dose of study drug; an additional ECG must be performed 1-3 hours after administration of first dose. *See Footnote m.*
- m: **INPATIENTS:** The Day 4 ECG in triplicate is required prior to the first dose of study drug and again within 1-3 hours after the first dose of study drug.  
**OUTPATIENTS:** The Day 4 ECG can be performed at the required study site visit 96 ± 24 hours after the first dose. *See Footnote c.* The Day 4 ECG in triplicate is required prior to the first dose of study drug and again within 1-3 hours after the first dose of study drug.
- n: A complete physical examination is performed at Baseline and directed physical examinations are performed thereafter.
- o: **INPATIENTS:** On Day 4, a directed physical examination will be performed.  
**OUTPATIENTS:** A directed physical examination will be performed at the study site visit scheduled 96 ± 24 hours after the first dose. *See Footnote c.*
- p: Blood samples sent to the local laboratory for the purposes of determining study eligibility must be repeated and sent to the central laboratory following enrollment. Collect blood and/or urine at LFU only if subject had an abnormal (high/low flag) result at TOC.
- q: **INPATIENTS:** On Day 4, blood and urine samples will be collected for safety laboratory evaluations.  
**OUTPATIENTS:** Blood and urine samples will be collected for safety laboratory evaluations at the study site visit scheduled 96 ± 24 hours after the first dose. *See Footnote c.*
- r: A urine pregnancy test will be performed at the site on all females unless surgically sterile or at least 2 years post-menopausal. A negative urine pregnancy test is required prior to randomization. Serum must be collected on Day 1 prior to 1st dose and sent to the central lab for confirmatory testing.
- s: Blood to be collected and sent to central laboratory for serologic tests for *M. pneumoniae*, *C. pneumoniae* and *L. pneumophila*.
- t: Collect blood samples (2 sets via peripheral venipuncture) for microbiologic culture and susceptibility testing at the local/regional lab at Baseline and as clinically indicated during the study. Repeat blood cultures after a positive result until sterilization is documented. If possible, subjects who are discontinued from study drug due to confirmed MRSA or MSSA bacteremia should have blood samples collected for microbiologic culture prior to switching to alternate appropriate therapy. All organisms isolated from blood cultures which are not considered contaminants will be sent to the central laboratory for confirmatory identification and susceptibility testing.
- u: All lower respiratory tract and expectorated sputum samples should be sent to the local/regional laboratory for Gram's stain, culture and susceptibility testing. A sputum sample will be taken at Screening for Gram's staining, culture and susceptibility testing at the local/regional laboratory. If a subject is unable to produce an adequate (> 25 polymorphonuclear [PMN] cells **AND** < 10 squamous epithelial cells per LPF) sputum sample at Screening, a specimen should be obtained, if possible, within 24 hours after the first dose of study drug. Gram's stain and culture results from the local/regional laboratory will be recorded in the eCRF. Slides (stained and unstained) will also be sent to the central laboratory for a confirmatory reading of the Gram's stain. If possible, subjects who are discontinued from study drug due to clinical failure should have repeat cultures collected for microbiologic culture prior to switching to alternate appropriate therapy. All organisms isolated from sputum samples, which are not considered contaminants, will be sent to the central laboratory for confirmatory identification and susceptibility testing. In addition, a portion of all Baseline sputum samples must be frozen until sent to the central laboratory for quantitative PCR. Subjects with a urinary antigen positive for *Legionella* spp. will also have a portion of their sputum sample sent frozen to the central laboratory for isolation of *L. pneumophila*.
- v: Collect pleural fluid samples and/or BAL only if medically indicated. Gram's stain samples, culture, and test the isolated pathogens for susceptibility. Pathogens isolated from pleural fluid and/or BAL samples will be sent to the central laboratory for confirmatory identification and susceptibility testing. If possible, pleural fluid samples should be incubated in blood culture bottles for optimal pathogen recovery.
- w: An oropharyngeal specimen (2 swabs) and a nasopharyngeal specimen (1 swab) will be collected and frozen until sent to the central laboratory. The oropharyngeal specimen will be used for culture of *M. pneumoniae* and identification by PCR. The nasopharyngeal specimen will be used for culture and identification by PCR of *S. pneumoniae*, and potentially, *H. influenzae*.
- x: Study personnel will administer the first dose of study drug at the study site, as soon as possible after the diagnosis of CABP and completion of all required pre-dose Day 1 procedures. On Day 1, if q12h dosing is not feasible, the 1st and 2nd doses may be administered as close as 8 hours apart, in order to allow 2 doses to be given on Day 1. In this circumstance, the subject's dosing schedule should be adjusted on Day 2 to a regular q12h morning and evening schedule. Subsequently, every effort should be made to maintain a q12h dosing schedule. When this is not possible, it is acceptable to administer doses within 4 hours of the scheduled dosing time (i.e., a minimum of 8 hours between doses). For Outpatients, or in the event a subject is discharged from the hospital during the study drug administration period, an adequate supply of study drug will be dispensed for self-administration at home. Subjects will be provided instructions regarding the dosing schedule. Subjects may self-administer oral study drug at home with the following exception: Study personnel will advise subjects who are

Outpatients that they must return to the study site to assess CABP signs and symptoms at  $96 \pm 24$  hours after the first dose of study drug. **See Footnote c.** Administration of study drug may occur on the same calendar day as EOT, and if so will be completed before EOT assessments begin.

- y: Collect blood samples for PK analysis relative to the first dose of study drug. Blood will be collected within 1 h pre-dose, 1-2 h post dose, and 3-4 h post dose, and 8-9 h post dose. INPATIENTS: PK sampling should occur on Day 4 but, if not feasible, it can be done relative to the first dose on Day 5; the 8-9 h post dose is required. OUTPATIENTS: PK sampling will be done during the  $96 \pm 24$  hours post 1st dose visit. The 8-9 h post dose sample is optional; however, it should be obtained if logistically feasible.
- z: Investigator to determine IACR - Success, Failure or Indeterminate (i.e., subject lost to follow up) at EOT and TOC and Sustained Success, Relapse or Indeterminate at LFU. The Investigator will not determine Clinical Response at TOC or LFU if the subject was previously deemed to have an IACR of Failure.

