# 6.5 Vital Signs and Oxygen Saturation

Vital signs (HR, BP, respiratory rate and body temperature) and oxygen saturation will be recorded at time points specified in Table 1. Blood pressure and heart rate assessments will be performed according to standard practice at the clinical sites. Vital signs associated with the highest temperature after the first dose of study drug will be recorded in the eCRF.

In addition, if the subject is receiving supplemental oxygen therapy, the amount given will be recorded in the eCRF.

All subjects will have vital signs and O2 saturation evaluated at Screening/Baseline and Day 1. If screening/baseline and Day 1 occur on the same calendar day, vital signs and O2 saturation do not need to be repeated. All subjects will also have assessments at EOT and TOC; at LFU, vital signs should be performed if medically indicated. If EOT and the last day of study drug are the same day, vital signs do not need to be repeated, they may be recorded once on that day (i.e., as part of the EOT assessment).

For Inpatients, in addition to the above time points, vital signs and O2 saturation will be measured daily and recorded. If multiple vital signs are taken on a study day, the highest

temperature and the vital signs associated with that high temperature will be recorded. For Outpatients, in addition to the above time points, vital signs and saturation will be measured at the study visit scheduled  $96 \pm 24$  hour after the first dose of study drug (see Section 6.1.1).

Vital signs measurements are to be repeated if clinically significant changes or machine errors occur. Out of range BP and HR will be repeated at the Investigator's discretion. Semi-supine BP and HR will be measured more frequently if warranted by the clinical condition of the subject.

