## 7.2 Visit Windows

### 7.2.1 Baseline

Unless otherwise stated below, baseline is defined as the last measurement prior to the first dose of study drug.

- For microbiological pathogen determination, baseline is defined as the 24-hour period prior to the administration of the first dose of study drug and the 24 hours after the first dose of study drug. A pathogen identified from a respiratory (pleural fluid, bronchoalveolar lavage (BAL), sputum), blood for culture, urine, nasopharyngeal or oropharyngeal specimen collected at baseline is considered a baseline pathogen. An atypical pathogen identified by serology is considered a baseline pathogen if the baseline

sample is collected in the 24-hour period prior to or the 24 hours after the administration of the first dose of study drug.

- For vital signs, baseline is defined as the Screening assessment (since time of assessment is not captured) as long as the date of collection is on or before the date of first dose of study drug.
- For ECGs, baseline is defined as the mean of the triplicates (or duplicate or single, if a triplicate is not obtained) from the last assessment prior to the first dose of study drug, including scheduled and unscheduled visits.
- If no study drug is received, baseline is defined as the measurement taken at the Screening Visit (ie, prior to the randomization date/time)

Study Day 1 is defined as the first calendar day of study drug administration (or the date of randomization if no study drug was received). The calendar day prior to the first dose of study drug (or randomization day if no study drug is received) is Study Day -1; there is no Study Day 0.

For all clinical assessments and procedures performed prior to the date of the first study drug administration, study day will be calculated as the date of the assessment minus the date of the first dose of study drug. For all clinical assessments and procedures performed on or after the date of the first dose of study drug, study day will be calculated as the date of the assessment minus the date of the first dose of study drug, plus 1.

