### **7.2.3 Unscheduled Assessments**

If no scheduled visit was done, but an unscheduled safety assessment was done in the window of the scheduled assessment (for the specific safety parameter), the unscheduled assessment should be used as described in Appendix D. If more than 1 measurement is taken during the visit window (a scheduled visit and an unscheduled visit), the value taken on the scheduled visit will be utilized. If more than one unscheduled assessment is completed in the visit window of the scheduled assessment (and no scheduled assessment), the earliest should be used. All unscheduled visits not satisfying the analysis visit condition as described in Appendix D will be referred to as “Unscheduled” as their analysis visit designation. For overall worst post-baseline analyses (i.e. minimum, maximum, highest, lowest, any post-baseline, and PCS), all assessments including those obtained on unscheduled (i.e. analysis visit “Unscheduled”) and scheduled visits (e.g., analysis visits “Baseline”, “Day 1”, “Day 4”, “TOC”, “EOT” and “LFU”) will be included. See Section 8.7.2 for a discussion of when to use central and local safety laboratory values.

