### 8.7.4 Vital Signs

Descriptive statistics for temperature, respiratory rate, heart rate, diastolic blood pressure, systolic blood pressure, and the change from baseline at each post-baseline visit will be summarized by treatment group for all subjects in the Safety Analysis Set. Change from baseline will be calculated for each subject at the specified visit as the value at the specified visit minus the baseline value. The change from baseline to the minimum and maximum post-baseline values will also be summarized by treatment group. Change from baseline will be calculated for each subject as the minimum or maximum post-baseline value minus the baseline value. Baseline is defined as the last assessment prior to Day 1.

Post-baseline vital signs will be defined as high or low if the criterion value listed in Table 11 is met. All vital signs will be presented in a listing with a flag for high and low indicating the criterion value was met. PCS is defined as meeting both the criterion value and the change from baseline criterion listed in Table 11. The number and percentage of subjects with any post-baseline PCS vital sign will be presented by treatment group. The overall post-baseline incidence of PCS values, which includes values from unscheduled post-baseline visits, will be summarized by treatment group for the Safety Analysis Set, and all PCS vital sign values will be listed and flagged in by subject listings.

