## APPENDIX D: SAFETY ASSESSMENT WINDOWS

### Vital Signs:

Analysis Visit	Study Visit	Target Day	If scheduled study visit assessment not available:	
			Consider Unscheduled assessment for Analysis Visit?	Study Days acceptable for Analysis Visit 
Baseline	Screening 	-	No	-
Day 1	Day 1	1	Yes	1
Day 2	Day 2	2	Yes	2
Day 3	Day 3	3	Yes	3
Day 4	Day 4	4	Yes	4
Day 5	Day 5	5	Yes	5
Day 6	Day 6	6	Yes	6
Day 7	Day 7	7	Yes	7
EOT	EOT	-	Yes	within 2 days after the last dose of study drug (i.e., last day of study drug through 2 subsequent calendar days)
TOC	TOC	-	Yes	5-10 days after last dose of study drug
Unscheduled 	-	-	Yes	

Notes: EOT: End of Treatment; TOC: Test of Cure; N/A: Not applicable.

 Except for Baseline, if more than 1 measurement is taken during the visit window (and no scheduled is taken) the earliest value will be analyzed..

 Provided the date of collection is on or before the date of first dose

 Any unscheduled assessments not meeting the criteria for an analysis visit.

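### Vital signs: Day 1 is analysed as a post-baseline visit with no pre/post-dose condition, so pre-treatment values can enter the change, worst-value and PCS summaries

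*SAP*

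**What the plan says.** **When Day 1 vital signs are taken.** Footnote b of the schedule (SAP Appendix A, and Protocol Table 1) sets a general rule: "Assessments/ procedures on Day 1 should be performed prior to first dose". Footnote i, which is specific to vital signs, contains a same-day waiver. It begins "If screening/baseline and Day 1 occur on the same calendar day, vital signs and" goes on to say that these and oxygen saturation need no repeat.

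**Which set is recorded.** The same footnote i also instructs: "Record the vital signs associated with the highest temperature after the first dose of study drug". Protocol 6.5 agrees: "Vital signs associated with the highest temperature after the first dose of study drug will be recorded in the eCRF". For inpatients with several readings on a study day, footnote i asks for the set at that day's highest temperature, with no reference to dosing.

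**Baseline.** SAP 7.2.1: "For vital signs, baseline is defined as the Screening assessment (since time of assessment is not captured"), provided the collection date is on or before the date of first dose.

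**Analysis.** In SAP Appendix D (Vital Signs), Baseline comes from Screening, and Day 1 is a separate analysis visit with the row "Day 1 Day 1 1 Yes 1". That is target day 1, unscheduled readings allowed, Study Day 1 accepted. SAP 8.7.4 says that the "change from baseline at each post-baseline visit will be summarized by treatment group", and adds minimum/maximum change and any post-baseline PCS value. SAP 7.2.3 reads "For overall worst post-baseline analyses (i.e. minimum, maximum, highest, lowest, any post-baseline, and PCS), all assessments including those obtained on unscheduled" and scheduled visits are included; its examples name Day 1. Table 11 is titled as criteria for treatment-emergent PCS vital signs.

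**The concern.** A value measured before the first dose cannot be treatment-emergent. If the Day 1 record is pre-dose, the Day 1 change row shows movement between Screening and dosing in acutely ill, untreated subjects. A swing in heart rate or blood pressure in that interval that meets Table 11 would be counted as a treatment-emergent PCS event. With no time recorded, programming cannot separate such values from genuine post-dose ones.

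At stake is how the descriptive vital-sign safety tables are read: PCS percentages too high in both arms, and a between-arm ratio pulled towards 1.

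**Working it through.** **Step 1. Is the recorded Day 1 set pre-dose or post-dose?** The documents point both ways.

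| Source | Implies |
|---|---|
| Footnote b | Pre-dose (general rule for Day 1) |
| Footnote i, same-day waiver | Pre-dose: a Screening reading, necessarily before dosing, can stand in only for another pre-dose reading |
| Footnote i and Protocol 6.5, recording rule | Post-dose |
| Footnote i, inpatients with several readings in a day | Either |

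**Step 2. Does any analysis rule sort them?** Not for vital signs. Appendix D's Day 1 row has no dosing condition, and an unscheduled Study Day 1 reading can fill it. The other safety domains do separate the two:

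- ECG: a Day 1 pre-dose tracing belongs to Baseline, and the analysis visit is labelled Day 1 post dose.
- Laboratory: Baseline requires date and time at or before the first dose, and there is no Day 1 visit.

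**Step 3. Would correcting nearby wording cure it?** No. SAP 7.2.3 also lists Baseline among the visits feeding worst post-baseline analyses, and 8.7.4 words the baseline differently from 7.2.1 (last assessment before Day 1). Correcting either leaves Day 1 as a post-baseline visit.

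**Step 4. How large could the effect be?** The plan has no figure to reproduce, and the documents give no vital-sign variances or PCS rates. What follows is illustrative.

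*(a) Chance of a spurious PCS value.* Let a subject's mean be t ~ N(μ, SD between), with Screening and pre-dose Day 1 readings each equal to t plus independent noise N(0, SD within). Count Table 11 events by simulation. These rates apply only to subjects with a separate pre-dose Day 1 record; the counts per 369 assume that everyone has one.

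| Criterion | Assumed μ / SD between / SD within | Rate | Per 369 |
|---|---|---|---|
| Heart rate ≥120 and rise ≥15 | 95 / 14 / 6 | 0.54% | 2.0 |
| | 95 / 14 / 8 | 1.52% | 5.6 |
| | 100 / 15 / 8 | 2.50% | 9.2 |
| | 100 / 15 / 10 | 4.32% | 15.9 |
| Systolic <90 and fall ≥20 | 125 / 16 / 8 | 0.35% | 1.3 |
| | 120 / 18 / 10 | 1.52% | 5.6 |
| | 120 / 18 / 12 | 2.57% | 9.5 |

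*(b) Effect on reported rates.* Let p be the true post-dose PCS rate and q the spurious pre-dose rate over all subjects. If the two are independent, the reported rate is 1 − (1 − p)(1 − q). The difference between arms is then the true difference times (1 − q). Assume p = 4% and 2%.

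| q | Reported rates | Ratio | Difference (points) |
|---|---|---|---|
| 0 | 4.00% vs 2.00% | 2.00 | 2.00 |
| 0.5% | 4.48% vs 2.49% | 1.80 | 1.99 |
| 1% | 4.96% vs 2.98% | 1.66 | 1.98 |
| 3% | 6.88% vs 4.94% | 1.39 | 1.94 |

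*(c) Allowing for partial exposure.* Write q = f × p0, where f is the share of subjects with a separate pre-dose Day 1 record and p0 the spurious rate among them. For f = 20% to 100% and p0 = 0.5% to 2%, the ratio runs from 1.95 (f = 20%, p0 = 0.5%) to 1.49 (f = 100%, p0 = 2%), and the difference stays between 2.00 and 1.96 points.

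**The case against.** The strongest reply is that the specific rule overrides the general one. Footnote b is a default that other items already override: footnote l requires a Day 1 ECG after dosing, and footnote y requires post-dose PK samples. Footnote i and Protocol 6.5 are specific to vital signs and call for a set taken after the first dose. On that reading Day 1 is correctly post-baseline.

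This stands far enough to defeat a stronger reading. A reader might infer that Day 1 vital signs simply are pre-treatment, and that the Day 1 change row describes untreated change. The documents do not support that, because some or many Day 1 records may be post-dose. The reply does not settle the matter, however: the waiver makes sense only for a pre-dose set, and the inpatient highest-temperature rule ignores dosing.

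Other points that stand:

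- Screening is within 24 hours of the first dose, and same-day subjects may have no separate Day 1 record, so exposure is limited and unknown.
- The spurious rates are assumptions. If f were 30%, q = 3% would need p0 = 3% / 30% = 10%. Positive correlation between pre-dose and post-dose events within a subject would shrink the inflation further.
- SAP 8.7.4 plans counts and percentages by arm, with no ratio and no test. A reader might infer that a drug effect would be materially diluted; the nearly constant risk difference argues against this.
- The visit list in 7.2.3 is generic across safety parameters, so on its own it is weak evidence of intent for vital signs.
- Dropping every Day 1 value not proven post-dose could remove genuine first-day reactions. Unscheduled Day 1 readings may be repeats prompted by clinically significant changes (Protocol 6.5).

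**Conclusion.** The point holds as a possibility that the plan leaves open: pre-treatment Day 1 vital signs can enter post-baseline change, minimum/maximum and treatment-emergent PCS counts, and nothing in the SAP detects or removes them. The cause is a conflict in the recording rules combined with an uncaptured assessment time.

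The consequence is modest. It is confined to descriptive safety tables. Pre-dose values cannot depend on the assigned drug, so both arms should be inflated alike. On the assumed rates the ratio could move noticeably while the risk difference moves by at most 0.06 points. ECR, IACR and the non-inferiority tests are unaffected. The size rests entirely on assumed PCS rates, assumed variances, independence and an unknown exposed fraction. The inconsistency itself rests on the text alone. It is worth correcting because the remedy is cheap.

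**What to change.** 1. Reconcile footnotes b and i with Protocol 6.5, stating which Day 1 vital-sign set is recorded.
2. Add a pre/post-dose indicator, or a time, to the Day 1 vital-sign page.
3. In SAP Appendix D (Vital Signs) and 8.7.4, exclude Day 1 values known to be pre-dose from post-baseline change, minimum/maximum and PCS. Keep those known to be post-dose.
4. Where timing is unknown, show Day 1 as its own labelled row, and present the worst-value and PCS summaries both with and without those values, so that first-day post-dose events are not lost.

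Cost: one data field and one extra set of tables. A new field does not by itself classify records already entered; unless their timing can be established, those fall under item 4.
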